### 11.5.2. Safety Analyses

The ITT population will be used for the analysis of safety data.

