# 9.6. Time Period and Frequency of Detecting AEs and SAEs

AE/SAE will be detected and recorded from the time a subject consents to participate in the study until he or she has completed the study (including a 28-day follow-up period). All SAEs assessed as related to study participation (e.g., protocol-mandated procedures, invasive tests, or change in existing therapy) or related to a GSK concomitant medication, will be reported promptly to GSK.

The investigator will monitor all ongoing AEs/SAEs after discontinuation of study treatment until the AE/SAE is resolved or until the subject is lost to follow-up.

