## 9.7.1. Time period for collecting pregnancy information

The time period for collecting pregnancy information is identical to the time period for collecting AEs, as stated in Section 9 "Time Period, and Frequency of Detecting AEs and SAEs", from first dose of study treatment to 28 days after last dose.

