## Intent-to-treat population

The intent-to-treat population will be defined as all subjects entered into the study. This population will be used to assess the sensitivity of the efficacy and safety analyses to protocol violations.

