## Safety Population

The safety population will be defined as all subjects who received at least one dose of study drug. The safety population will be used for all demographic, background and adverse event summaries and analyses. Subjects who do not receive treatment according to assignment will be grouped according to treatment received.

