#### Adverse events

Adverse events (AEs) will be coded using the standard GlaxoSmithKline Medical Dictionary for Regulatory Activities (MedDRA) dictionary, and grouped by system organ class. AE terms may also be aggregated according to the Aggregation Guidelines for AE Terms in Lapatinib Studies.

Events will be summarised by frequency and proportion of total subjects, by system organ class and preferred term. Separate summaries will be given for all AEs, drug-related AEs, serious AEs leading to discontinuation of investigational product.

If the AE is listed in the NCI CTCAE table, the maximum grade will be summarised.

The incidence of deaths will also be reported and the primary cause of death summarised.

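### Section 11.5.2 names the ITT set for safety data although Section 11.3.1 assigns adverse events to the Safety population; if any entered subject is never dosed, drug-related adverse event rates are understated

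*Protocol*

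**What the plan says.** Protocol Section 11.3.1 defines two relevant sets. For the first: "The intent-to-treat population will be defined as all subjects entered into the study". Its purpose is stated next: "This population will be used to assess the sensitivity of the efficacy and safety analyses to protocol violations". For the second: "The safety population will be defined as all subjects who received at least one dose of study drug". Its purpose is also stated: "The safety population will be used for all demographic, background and adverse event summaries and analyses".

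Section 11.5.2 then opens with a different assignment: "The ITT population will be used for the analysis of safety data". That sentence is unqualified and heads the subsections on exposure, adverse events, laboratory evaluations and other safety measures. Within it, the adverse event subsection fixes the form of the rate: "Events will be summarised by frequency and proportion of total subjects, by system organ class and preferred term".

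The protocol does not define 'entered', and no section ranks 11.5.2 against 11.3.1.

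**The concern.** Two sections assign different populations to the adverse event tables, and both cannot be followed. The sets differ by definition: one requires a dose and the other does not. Section 11.5.2 makes the set that 11.3.1 reserves for sensitivity work into the main set for safety.

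This matters because safety is a named secondary objective and the study is single-arm. With no comparator, the absolute incidence is the safety result. A subject who never took lapatinib cannot have a drug-related or treatment-emergent event, so including that subject can only lower those incidences. In an open-label trial, an unresolved choice of denominator could also be settled after the data have been seen.

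**Working it through.** The protocol states no adverse event rate and no expected number of undosed subjects, so there is no figure of its own to reproduce. The check has two parts: a comparison of the sections, and the arithmetic of dilution over an assumed range.

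**Comparison of the sections**

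- Adverse events: 11.3.1 says Safety population; 11.5.2 says ITT. This is a direct contradiction.
- Role of ITT in safety: 11.3.1 says sensitivity; 11.5.2 says the analysis itself. Also a contradiction.
- Laboratory values, ECG and ECHO/MUGA: 11.3.1 does not list these under the Safety population, so 11.5.2 is the only main assignment. This is not a contradiction, but these summaries then default to the set without a dosing condition.

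**Inputs for the arithmetic**

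- Treated subjects: 62 at most, 31 per stratum (Protocol Summary; Sections 6.2 and 11.2.1). These passages describe subjects treated, so undosed subjects are counted in addition to 62.
- Entered but never dosed, k: not given. Assumed range 0 to 8.
- True incidence among dosed subjects: not given. 30% is assumed for illustration.

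**Formula**, for an event that can occur only after dosing:

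ITT rate = Safety rate × treated / (treated + k)

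**Both strata together, 62 treated**

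- k = 0: 62/62 = 1.000, so 30% reads 30.0%
- k = 1: 62/63 = 0.984, so 29.5%
- k = 2: 62/64 = 0.969, so 29.1%
- k = 3: 62/65 = 0.954, so 28.6%
- k = 6: 62/68 = 0.912, so 27.4%
- k = 8: 62/70 = 0.886, so 26.6%

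**One stratum, 31 treated**

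- k = 1: 31/32 = 0.969, so 29.1%
- k = 2: 31/33 = 0.939, so 28.2%
- k = 3: 31/34 = 0.912, so 27.4%

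**If 'entered' were read as consented to screening.** Section 2.2.1 hypothesises that about 25% of patients acquire HER-2 amplification, and Section 2.1 cites a study with 9 of 24 (37.5%) on circulating tumour cells. Take these as an assumed range for the share passing the CTC test. They are HER-2 figures; applying them to the EGFR stratum is a further assumption, and other screening failures are ignored. Then 62 treated implies 62/0.375 ≈ 165 to 62/0.25 = 248 consented. The factor is 0.375 to 0.25, and 30% would read 11.3% to 7.5%.

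**All-cause events.** Section 9.6 says: "AE/SAE will be detected and recorded from the time a subject consents to participate in the study". Section 9.7.1 describes the adverse event period as running "from first dose of study treatment to 28 days after last dose". If 9.6 governs, an undosed subject can contribute an event. Suppose 20 of 31 dosed subjects have an event and 2 undosed subjects each have one before any dose (assumed). The Safety rate is 20/31 = 64.5% and the ITT rate is 22/33 = 66.7%. The all-cause rate rises. The downward direction is therefore certain only for events that need exposure.

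**The case against.** The strongest case on the other side is that the two sets may turn out identical. Section 5.1 has drug dispensed on day 1, after eligibility is confirmed and screening results are reviewed. If 'entered' means registered at that point, few or no entered subjects will be undosed and the bias is nil or small. The go/no-go rule also rests on response rate, so no decision in Section 11.2.1 changes. Both points stand. They limit the size of the problem but do not remove the contradiction, since the protocol neither defines 'entered' nor says which section prevails.

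A reader might infer more than the protocol supports, in five ways:

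- *Every toxicity rate is understated.* This needs at least one undosed subject, and the protocol gives no count. All-cause rates need not fall if events are collected from consent.
- *The 28-day screening window shows that undosed subjects will be in the ITT set.* Screening precedes eligibility confirmation. It produces undosed ITT members only if 'entered' is read as consented.
- *LVEF and liver results are diluted too.* Section 11.5.2 reports out-of-range laboratory results as a proportion of values, and cardiac assessments as summaries of scheduled results. A subject with no on-treatment values does not dilute these. The concern reaches such findings only where they are counted as adverse events.
- *Safety rates could not be related to exposure.* The exposure summary reports the number of subjects given lapatinib, so the dosed count remains visible.
- *The undosed should be subtracted from 62.* The protocol describes 62 as subjects treated, so the undosed are additional.

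**Conclusion.** The contradiction is certain and stands in the current text. Section 11.5.2 names a population that includes unexposed subjects for an analysis that 11.3.1 gives to dosed subjects only.

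The numerical consequence is conditional. It is zero if every entered subject is dosed. With 62 treated and an assumed 1 to 3 further subjects undosed, drug-related and treatment-emergent incidences are understated by about 1.6% to 4.6% in relative terms; with 8 undosed, by about 11%. On an assumed 30% incidence, that is 0.5 to 1.4 percentage points, and about 3.4 points with 8 undosed. A large effect arises only if 'entered' is taken to mean consented to screening, a reading that the protocol neither adopts nor excludes.

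The point should be corrected because a stated rule puts the wrong subjects in the denominator of a single-arm safety result. It does not affect the primary efficacy conclusion.

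**What to change.** Replace the opening sentence of Section 11.5.2 with: *The Safety population (all subjects who received at least one dose) will be used for all safety analyses.* This resolves the conflict for adverse events and also gives the laboratory, ECG and cardiac summaries, which 11.3.1 does not mention, a population of dosed subjects.

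In Section 11.3.1, define 'entered', for example by stating the step (consent, registration or confirmation of eligibility) that places a subject in the ITT set. The sensitivity role of ITT can stay; it does not conflict with the Safety population as the main set.

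The cost is one replaced sentence and one added definition, with no effect on patients, visits or sample size. Reported adverse event rates may become slightly less favourable than under the ITT denominator.

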#### Extent of Exposure

The number of subjects administered lapatinib will be summarised according to the duration of treatment. The daily dose and cumulative dose of lapatinib will also be summarised.

#### Adverse events

Adverse events (AEs) will be coded using the standard GlaxoSmithKline Medical Dictionary for Regulatory Activities (MedDRA) dictionary, and grouped by system organ class. AE terms may also be aggregated according to the Aggregation Guidelines for AE Terms in Lapatinib Studies.

Events will be summarised by frequency and proportion of total subjects, by system organ class and preferred term. Separate summaries will be given for all AEs, drug-related AEs, serious AEs leading to discontinuation of investigational product.

If the AE is listed in the NCI CTCAE table, the maximum grade will be summarised.

The incidence of deaths will also be reported and the primary cause of death summarised.

#### **Clinical Laboratory Evaluations**

Haematology and clinical chemistry data will be summarised at each scheduled assessment according to NCI CTCAE toxicity grade. The proportion of values lying outside the reference range will also be presented.

#### **Other Safety Measures**

The results of scheduled assessment of body weight, vital sign, 12-lead ECG, echocardiogram (or MUGA scan) and performance status will be summarised. Further details will be provided in the Statistical Analysis Plan.

# 12. STUDY CONDUCT CONSIDERATIONS

Prior to initiation of a study site, GSK will obtain approval from the appropriate regulatory agency to conduct the study in accordance with applicable country-specific regulatory requirements.

The study will be conducted in accordance with Good Clinical Practice (GCP), all applicable subject privacy requirements, and the guiding principles of the declaration of Helsinki, including, but not limited to:

- Institutional Review Board (IRB)/Independent Ethics Committee (IEC) review and approval of study protocol and any subsequent amendments.
- Subject informed consent.
- Investigator reporting requirements.

GSK will provide full details of the above procedures, either verbally, in writing, or both.

Written informed consent must be obtained from each subject prior to participation in the study.

# 12.1. Quality Control (Study Monitoring)

In accordance with applicable regulations, GCP, and GSK procedures, GSK monitors will contact the site prior to the start of the study to review with the site staff the protocol, study requirements, and their responsibilities to satisfy regulatory, ethical, and GSK requirements. When reviewing data collection procedures, the discussion will include identification, agreement and documentation of data items for which the CRF will serve as the source document.

GSK will monitor the study to ensure that the:

- Data are authentic, accurate, and complete.
- Safety and rights of subjects are being protected.
- Study is conducted in accordance with the currently approved protocol and any other study agreements, GCP, and all applicable regulatory requirements.

The investigator and the head of the medical institution (where applicable) agrees to allow the monitor direct access to all relevant documents

# 12.2. Quality Assurance

To ensure compliance with GCP and all applicable regulatory requirements, GSK may conduct a quality assurance audit of the site records, and the regulatory agencies may conduct a regulatory inspection at any time during or after completion of the study. In the event of an audit or inspection, the investigator (and institution) must agree to grant the auditor(s) and inspector(s) direct access to all relevant documents and to allocate their time and the time of their staff to discuss any findings/relevant issues.

## 12.3. Study and Site Closure

Upon completion or termination of the study, the GSK monitor will conduct site closure activities with the investigator or site staff (as appropriate), in accordance with applicable regulations, GCP, and GSK Standard Operating Procedures.

GSK reserves the right to temporarily suspend or terminate the study at any time for reasons including (but not limited to) safety issues, ethical issues, or severe noncompliance. If GSK determines that such action is required, GSK will discuss the reasons for taking such action with the investigator or head of the medical institution (where applicable). When feasible, GSK will provide advance notice to the investigator or head of the medical institution of the impending action.

If a study is suspended or terminated for safety reasons, GSK will promptly inform all investigators, heads of the medical institutions (where applicable),and/or institutions conducting the study. GSK will also promptly inform the relevant regulatory authorities of the suspension/termination along with the reasons for such action. Where required by applicable regulations, the investigator or head of the medical institution must inform the IRB/IEC promptly and provide the reason(s) for the suspension/termination.

# 12.4. Records Retention

Following closure of the study, the investigator or head of the medical institution (where applicable) must maintain all site study records (except for those required by local regulations to be maintained elsewhere) in a safe and secure location. The records must be easily accessible when needed (e.g., for a GSK audit or regulatory inspection) and must be available for review in conjunction with assessment of the facility, supporting systems, and relevant site staff.

Where permitted by local laws/regulations or institutional policy, some or all of the records may be maintained in a format other than hard copy (e.g., microfiche, scanned, electronic); however, caution must be exercised before such action is taken. The investigator must ensure that all reproductions are legible and are a true and accurate copy of the original. In addition, they must meet accessibility and retrieval standards, including regeneration of a hard copy, if required. The investigator must also ensure that an acceptable back-up of the reproductions exists and that there is an acceptable quality control procedure in place for creating the reproductions.

GSK will inform the investigator of the time period for retaining the site records in order to comply with all applicable regulatory requirements. The minimum retention time will meet the strictest standard applicable to a particular site, as dictated by local laws/regulations, GSK standard operating procedures, and/or institutional requirements, otherwise, the retention period will default to 15 years.

The investigator must notify GSK of any changes in the archival arrangements, including, but not limited to archival of records at an off-site facility or transfer of ownership of the records in the event that the investigator is no longer associated with the site.

## 12.5. **Provision of Study Results and Information to Investigators**

Where required by applicable regulatory requirements, an investigator signatory will be identified for the approval of the clinical study report. The investigator will be provided reasonable access to statistical tables, figures, and relevant reports and will have the opportunity to review the complete study results at a GSK site or other mutually-agreeable location.

Upon completion of the clinical study report, GSK will provide the investigator with the full summary of the study results. The investigator is encouraged to share the summary results with the study subjects, as appropriate.

# 12.6. Provision of Study Results and Information to Investigator

Where required by applicable regulatory requirements, an investigator signatory will be identified for the approval of the clinical study report. The investigator will be provided reasonable access to statistical tables, figures, and relevant reports and will have the opportunity to review the complete study results at a GSK site or other mutually-agreeable location.

Upon completion of the clinical study report, GSK will provide the investigator with the full summary of the study results. The investigator is encouraged to share the summary results with the study subjects, as appropriate.

# 13. PHARMACOGENETICS RESEARCH

## 13.1. Pharmacogenetics – Background

Pharmacogenetics (PGx) is the study of variability in drug handling or response due to hereditary factors in different populations. There is increasing evidence that an individual's genetic composition (i.e. his or her genotype) may impact drug handling or response, or clinical outcome. Genetic markers may be used to help understand and predict drug handling or response in terms of efficacy and/or safety and tolerability. Some reported examples of PGx analysis include:

Drug	Disease	Gene	Outcome
6-mercaptopurine (6- MP)	lymphoblastic leukemia	S-methyltransferase	Deficiency of the TPMT enzyme can be associated with toxicity and severe myelosuppression as patients are not able to sufficiently clear active thioguanine nucleotides (1, 2).
5-FU	Colorectal cancer	Dihydropyrimidine dehydrogenase (DPD)	Variants in the DPD gene result in little or no DPD and predisposition to toxicity to 5-FU (3-5)
Atomoxetine Desipramine	ADHD Depression	CYP2D6	Polymorphism in CYP2D6 result in different phenotypes; poor, intermediate, or extensive metabolizers. Poor metabolizing genotypes at risk of drug accumulation and associated toxicity (8-9)

A key component to successful PGx research is the collection of samples during the conduct of clinical studies. Collection of whole blood samples, even when no *a priori* hypothesis has been identified, may enable PGx analysis to be conducted if at any time it appears that there is a potential unexpected or unexplained variation in handling or response to GW572016.

# 13.2. Scope of PGx Analysis

PGx analysis may be conducted if unexplained variation in response to or handling of GW572016 (e.g., pharmacokinetics, efficacy and/or safety) that may be attributable to genetic variation are observed. In these circumstances, the analysis undertaken will be limited to PGx analysis of GW572016 handling or response and may include the evaluation of specific candidate genes, the conduct of a whole genome single nucleotide polymorphism (SNP) scan or other marker scan. Polymorphisms in target ErbB1, ErbB2, and other relevant genes previously associated with the adverse event in question will be evaluated. For the whole genome SNP scan approach, SNP or other genetic marker sets across the genome may be evaluated to identify those markers associated with differential drug handling or response.

The need to conduct PGx analysis may be identified after a study (or set of studies) of GW572016 has been completed and the study data reviewed. For this reason, samples may be kept for up to 15 years after the last subject completes the study or GSK may destroy the samples before then. In special cases, the samples may not be studied. This might happen if there are not enough subjects, if the study is stopped for other reasons, or if no questions are raised about how people respond to or handle GW572016.

In the performance of the PGx analysis, GSK may use subjects' medical information, samples and/or research results. This PGx research is not designed to determine whether other members of the subject's family are at risk of developing breast cancer or their response to or handling of GW572016.

## Sample Quality Control (QC)

If deoxyribonucleic acid (DNA) is extracted from blood samples taken from the clinical study, the DNA may be subjected to sample quality control (QC) analysis. This analysis will involve the genotyping of several genetic markers to confirm the integrity of individual samples. If inconsistencies are noted in the analysis, then those samples may be destroyed.

# **13.3.** Eligibility Criteria Considerations for PGx Participation

Any subject, who has given informed consent to participate in the clinical study, has met all the criteria required for entry into the clinical study may take part in the PGx research. Any subject who has received a bone marrow transplant must be excluded from the PGx research.

Subject participation in the PGx research is voluntary and refusal to participate will not indicate withdrawal from the clinical study. Refusal to participate will involve no penalty or loss of benefits to which the subject would otherwise be entitled.

No administration of investigational product beyond that detailed in the clinical study is associated with the PGx research.

Employees of GSK enrolled in the clinical study will not be eligible for participation in disease-based diagnostic research.

## 13.4. Pharmacogenetics Samples

In subjects who consent to PGx research, a 10 mL whole blood sample will be collected for the PGx research using a tube containing EDTA. The PGx sample is labeled (or "coded") with a study specific number that can be traced or linked back to the subject by the investigator or site staff. Coded samples do not carry personal identifiers (such as name or social security number). The blood sample will be taken on a single occasion unless a duplicate sample is required due to inability to utilize the original sample. It is recommended that the blood sample be taken at the first available opportunity, but may be taken at any time while the subject is participating in the clinical study. Sample collection and shipping instructions are provided in the Quest Manual.

